**Main Criteria for Exclusion**

1. Pregnant or nursing
2. History of organ transplantation, including renal transplantation
3. Currently on an organ transplant waiting list or there is a reasonable possibility of getting an

organ transplant within 6 months of screening.

4. Histological FSGS subtype of collapsing variant
5. Subjects who initiated, discontinued or changed dose of rituximab or other anti-CD20 monoclonal antibodies within 16 weeks (4 months) prior to screening are excluded. Subjects who initiated treatment with rituximab or other anti-CD20 monoclonal antibodies **>16 weeks (4 months)** prior to screening are permitted if deemed safe by the investigator and only if they are intended to remain on continued, unchanged therapy at a dosing interval that has been documented to achieve continuous B cell depletion for the given patient. UPCR and other urine protein assessments up to 1 year prior to screening (if available) that were performed in these patients as part of the clinical routine should be recorded in the medical history.
6. Subjects who discontinued Rituximab or other anti-CD20 monoclonal antibodies **>16 weeks (4 months) prior to screening** *without* confirmed recovery of CD20+ B cell population to within normal range are excluded. Subjects who discontinued rituximab or other anti-CD20 monoclonal antibodies **>16 weeks (4 months)** prior to screening *with* confirmed recovery of CD20+ B cell population to within normal range are permitted in the study. UPCR and other urine protein assessments up to 1 year prior to screening (if available) that were performed in these patients as part of the clinical routine should be recorded in the medical history.
7. Subjects who initiated or increased the dose of calcineurin inhibitors, or other immunotherapy, within 12 weeks prior to screening are excluded; dose reductions to maintain calcineurin inhibitors at optimal safe levels are permitted. Subjects who initiated a treatment with calcineurin inhibitors, or other immunotherapy **>12 weeks** are permitted. UPCR and other urine protein assessments up to 1 year prior to screening (if available) that were performed in these patients as part of the clinical routine should be recorded in the medical history.
8. Subjects taking glucocorticoids at dose greater than 10 mg/day prednisone equivalent within 4 weeks prior to screening are excluded.
9. Plasmapheresis within 12 weeks prior to screening
10. Body Mass Index (BMI)  $\geq 40$
11. Participated in any clinical study of an investigational product within 12 weeks prior to screening or within 5 half-lives after taking the last dose
12. Currently on dialysis or likely to require dialysis during the study.
13. History or presence of any form of cancer within the 5 years prior to screening, with the exception of excised basal cell or squamous cell carcinoma of the skin, or carcinoma *in situ* such as cervical or breast carcinoma *in situ* that has been excised or resected completely and is without evidence of local recurrence or metastasis
14. Positive HBV, HCV, or HIV viral screening test. Subjects who have received highly effective therapy for HCV demonstrated to have negative viral titers for at least 6 months following discontinuation of treatment, will be considered to have a negative HCV screening test weeks prior to screening
15. Evidence of tuberculosis based on interferon  $\gamma$  release assay (IGRA), tuberculin purified protein derivative (PPD) skin test, or chest radiography done during screening or within 6 weeks prior to screening
16. Evidence of hepatic disease; AST, ALT, alkaline phosphatase  $>2 \times$  ULN, or total bilirubin  $>2 \times$  ULN or INR  $> 1.5 \times$  ULN at screening with the exception that isolated INR elevation in

the absence of other significant liver enzyme abnormalities is explained by anticoagulant therapy, (e.g. warfarin).

17. Clinically significant peripheral neuropathy
18. Hematologic abnormalities as follows: Hb <8 g/dL, platelets <50,000, ANC <1000 cells/ $\mu$ L) at baseline
19. Abnormality of ECG at screening, assessed by the Investigator as clinically significant (e.g. QTcF greater than 450 msec).
20. History of alcohol or illicit drug abuse. Recreational use of cannabis is not excluded where legalized.
21. History of gastrointestinal conditions that may interfere with study medication compliance, e.g., severe gastroparesis, with regurgitation of food or oral medication
22. Known hypersensitivity to CCX140-B or inactive ingredients of the CCX140-B tablets (including microcrystalline cellulose, starch, crospovidone, magnesium stearate, or silicon dioxide)
23. Renal disease associated with disorders other than FSGS (e.g. lupus nephritis, C3 glomerulonephropathy) that is active, or has significant risk of progressing to end stage renal disease during the 12-week initial treatment phase of the study
24. History or presence of systemic disorder other than FSGS that requires, or is expected to require, systemic glucocorticoids or immune modulators; topical or inhaled corticosteroids and immune modulators are not excluded
25. History or presence of any medical condition or disease which, in the opinion of the Investigator, may place the subject at unacceptable risk for study participation
26. Subjects taking strong CYP3A4 inducers (e.g., phenytoin, rifampicin, carbamazepine, St. John's Wort) or strong CYP3A4 inhibitors (e.g., boceprevir, clarithromycin, conivaptan, grapefruit juice, indinavir, itraconazole, ketoconazole, lopinavir/ritonavir, mibefradil, nefazodone, nelfinavir, posaconazole, ritonavir, saquinavir, telaprevir, telithromycin, and voriconazole) within two weeks prior to screening.
27. Subjects taking lithium, pamidronate or interferon; subjects taking non-steroidal anti-inflammatory agents (NSAIDS) chronically (intermittent, i.e. occasional NSAIDS for pain or fever is discouraged, but is not excluded).

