Synopsis & Section 4.3: Exclusion Criteria	Evidence of hepatic disease; AST, ALT, alkaline phosphatase >2x ULN, or total bilirubin > 2x ULN or INR > 1.5 x ULN at baseline with the exception that isolated INR elevation in the absence of other significant liver enzyme abnormalities is explained by anticoagulant therapy, (e.g. warfarin).	Evidence of hepatic disease; AST, ALT, alkaline phosphatase >2x ULN, or total bilirubin > 2x ULN or INR > 1.5 x ULN at screening with the exception that isolated INR elevation in the absence of other significant liver enzyme abnormalities is explained by anticoagulant therapy, (e.g. warfarin).	Day 1 blood draws will be evaluated by a central laboratory and therefore won't be available in time for Day 1 dosing. Therefore, the screening assessments should be used.
Synopsis & Section 4.3: Exclusion Criteria - #20 and #27	23. History of alcohol or illicit drug abuse or of lithium, pamidronate, interferon or prescribed NSAIDS. Recreational use of cannabis is not excluded where legal.	20. History of alcohol or illicit drug abuse. Recreational use of cannabis is not excluded where legalized.  27. Subjects taking lithium, pamidromate or interferon; subjects taking non-steroidal anti-inflammatory agents (NSAIDS) chronically (intermittent, i.e. occasional NSAIDS for pain or fever is discouraged, but is not excluded).	Clarify drug exclusion and medication exclusion with two separate exclusion criteria
Synopsis & Section 4.3: Exclusion Criteria - #21	None	21. History of gastrointestinal conditions that may interfere with study medication compliance, e.g., severe gastroparesis, with regurgitation of food or oral medication	Added to make consistent with other CCXI protocols
Synopsis & Section 4.3: Exclusion Criteria - #26	22. Subject is taking strong CYP3A4 inducers (e.g., phenytoin, rifampicin,	26. Subjects taking strong CYP3A4 inducers (e.g., phenytoin, rifampicin, carbamazepine, St. John's Wort)	Strong CYP3A4 inhibitors are additionally excluded as concomitant medication due to

Section(s)	Original Text	Revised Text	Rationale for Change
	carbamazepine, St. John's Wort)	or strong CYP3A4 inhibitors (e.g., boceprevir, clarithromycin, conivaptan, grapefruit juice, indinavir, itraconazole, ketoconazole, lopinavir/ritonavir, mibefradil, nefazodone, neflifavir, posaconazole, ritonavir, saquinavir, telaprevir, telithromycin, and voriconazole) within two weeks prior to screening.	CYP3A4 metabolism of CCX_140-B.

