### Statistical Methods

Details of the statistical analysis will be provided in a separate statistical analysis plan (SAP), which will be written, finalized, and approved prior to database lock and will be included in the Clinical Study Report (CSR) for this protocol. The SAP will supersede the statistical analysis methods described in this clinical protocol. Any deviation from the protocol will be documented and described in the final report. If changes to principal features stated in the protocol are required, these will be documented in a protocol amendment. The final SAP will take into account any amendment to the protocol. Data analysis and writing of a CSR for all study data will be performed by the designated CRO in accordance with its SOPs. Analysis of PK and PD data, and writing of PK and PD reports will be performed by designated PK and PD teams in accordance with their standard operating procedures.

[figure not shown]
All continuous study assessments will be summarized by visit (as applicable) and change from baseline (baseline is typically defined as pre-dose evaluation on day 1 unless otherwise specified) to each post-baseline visit using descriptive statistics (n, mean, median, standard deviation, minimum, and maximum). All categorical study assessments will be summarized by visit (as applicable) using frequency counts and percentages.

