### 6.2. Study Day 1 (After Confirmation of Eligibility)

**All evaluations on day 1 (unless otherwise specified in the Day 1 section) will occur PRIOR to dosing to serve as baseline evaluations.**

1. Enroll study subject and obtain enrollment ID code
2. Full Physical Examination and Vital Signs including height, weight, heart rate, respiratory rate and body temperature
3. 24 hour urine collection for UPCR, UACR and total protein. *Subject starts 24hr. collection after the first void in the morning of the day prior to the visit day and should bring the 24hr collection (including first morning void on the visit day) to the visit. Sites need to contact the subject prior to the visit day as a reminder to start the 24 hr. urine collection*
4. AIDS Clinical Trials Group Brief Peripheral Neuropathy Screening Tool (ACTG BPNST)

5. Leg circumference and bioimpedance to assess edema
6. Triplicate 12-Lead ECG
7. Pregnancy Test for women of childbearing potential
8. Hematology, Serum Chemistry, Urinalysis
9. 24 hour urine collection for UPCR, UACR and total protein. *Subject starts 24hr. collection after the first void in the morning of the day prior to the visit day and should bring the 24hr collection (including first morning void on the visit day) to the visit. Sites need to contact the subject prior to the visit day as a reminder to start the 24 hr. urine collection. Please be reminded that a 24 hr. urine collection at baseline (Study day 1) and at week 12 are mandatory.*
10. SF-36 v2 and EQ-5D-5L
11. Dispense diaries and *Directions for Use* along with a 30 day supply of CCX140-B bottles.
12. Pharmacokinetics (time 0, 0.5, 1, 2, 3, 4 & 6 hours post dose), the time 0 sample is to be collected just prior to administration of the first dose of CCX140-B. Subjects must fast prior to the time 0, 0.5 and 1 hour PK and can consume food immediately after the 1 hour PK blood draw.
13. PD (plasma, serum and urine and whole blood for the lymphocyte subset and DNA)
14. Concomitant medications- verify and document any new medications that subject has started since the previous visit.
15. Adverse Events- record all adverse events starting with first dose of study medication and serious adverse events starting after administration of Informed Consent.

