### 8.2.2. Secondary Endpoint Analysis

Secondary endpoints include:

- Achievement of Partial Remission (includes all of the following)
  - reduction from baseline by  $\geq 50$  percent in UPCR
  - reduction in UPCR to a level that is  $< 3.5$  g/g at week 12
  - subject may not be a treatment failure
- Achievement of Complete Remission (includes all of the following) at week 12
  - reduction in UPCR to  $< 0.3$  g/g
  - serum albumin within normal range
  - for patients with abnormal serum creatinine levels at baseline, return to normal levels for that age group
  - for patients with normal serum creatinine levels at baseline, final value within 20% of baseline levels
  - subject may not be a treatment failure
- Change from baseline of UPCR in subjects treated with CCX140-B over time
- The proportion of subjects with partial remission at any time during the treatment period.
- The proportion of subjects with complete remission at any time during the treatment period.
- Time to Partial Remission (PR) or Complete Remission (CR)
- Change from baseline in renal function, based on eGFR (calculated using the CKD-EPI Cystatin C equation ([Dharnidharka VR, et al, 2002](#)), the CKD-EPI Creatinine equation ([Schwartz GJ, et al. 2016](#), [Selistre L et al 2016](#)), CKD-EPI Creatinine-Cystatin C equation ([Stevens et al., 2008](#)) and MDRD Creatinine equation ([Levey et al. 1999](#), [Levey et al. 2006](#)) over time
- Change over time in total 24 hour urine protein excretion

- Change from baseline in serum albumin over time
- Change in UACR from baseline over time
- Time to investigator or physician initiation of rescue therapy including glucocorticoids, new immunosuppressive agents or new major treatment modalities (e.g. plasmapheresis, dialysis)
- Duration between achievement of remission and relapse or treatment failure
- Changes over time in Health Quality Assessment (SF-36 v2 and EQ-5D-5L)

Change from baseline will be summarized with descriptive statistics (mean, SD, median and range) and 95% confidence interval for the mean. Baseline is defined as the last assessment prior to the first dose of the study drug.

Time to PR or CR and duration between achievement of remission and relapse or treatment failure will be summarized with the Kaplan-Meier estimate for the median and quartiles.

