### 3.1.3 *Definition of Baseline*

Baseline is defined as the last assessment prior to the first dose of study drug.

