### 3.6.2 Clinical Laboratory Tests

Blood and urine samples for clinical laboratory tests will be collected at Screening, Day 1, Day 15, Day 29, Day 57, Day 85 (Week 12), Week 16, Week 20, Week 24, Week 28, Week 32, Week 36, Week 40, Week 44, Week 48, Week 52, Early Termination (if applicable), and follow-up visit. Midstream spot urine void for UPCR during the site visits will be collected at every timepoint during the study. All chemistry, hematology, and urinalysis tests will be processed by a central laboratory. Local laboratory data will be listed.

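### Exclusion criterion 18 sets its haemoglobin, platelet and neutrophil limits at baseline (the Day 1 draw), whose central-laboratory result is not back when eligibility is decided or the first dose is given

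*Protocol*

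**What the plan says.** Criterion 18 appears in the synopsis (Main Criteria for Exclusion) and in protocol Section 4.3 with the same limits: "Hematologic abnormalities as follows: Hb <8 g/dL, platelets <50,000, ANC <1000". In both places the sentence closes by fixing the time point at baseline. Criteria 16 (hepatic) and 19 (ECG) refer to screening instead.

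Baseline is described in four places that bear on haematology:

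- Synopsis, Statistical Methods: "baseline is typically defined as pre-dose evaluation on day 1 unless otherwise specified".
- Protocol Section 6.2, on the Day 1 evaluations, which include haematology: they "will occur PRIOR to dosing to serve as baseline evaluations".
- Protocol Section 8.2.2: "Baseline is defined as the last assessment prior to the first dose of the study drug".
- SAP Section 3.1.3: "Baseline is defined as the last assessment prior to the first dose of study drug".

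On laboratory handling, SAP Section 3.6.2 says: "All chemistry, hematology, and urinalysis tests will be processed by a central laboratory". In the Amendment 1.0 summary of changes, the reason given for moving hepatic criterion 16 to screening is: "Day 1 blood draws will be evaluated by a central laboratory and therefore won't be available in time for Day 1 dosing". The sponsor's conclusion follows: "Therefore, the screening assessments should be used".

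**The concern.** An entry limit works only if its result is known when the entry decision is made. Criterion 18 points to a result that, on the sponsor's own account of laboratory turnaround, arrives after the first dose. A site that follows the text literally has two options. It can leave the limit unapplied at entry, or it can apply it when the Day 1 result comes back and find that a subject already on drug was ineligible. Section 8.9 gives enrolment of ineligible subjects as an example of a major deviation, so the second option would create deviations that the site could not have prevented.

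Haemoglobin is not an incidental parameter here. Section 1.3 reports anaemia in every species studied, bases the rat no-adverse-effect level on it, and regards it as likely to carry over to humans. Criterion 18 is the only numerical entry limit on haemoglobin in the protocol.

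**Working it through.** The plan gives no figure to reproduce, and the point involves no sample size, power or error rate. The check is of sequence, from the documents side by side.

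1. **Time point named.** Criterion 18 says baseline in both places. It carries no definition of its own and does not mention screening.

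2. **What baseline means for haematology.** The synopsis makes it the Day 1 pre-dose evaluation unless something else is specified, and criterion 18 specifies nothing else. Section 6.2 makes the Day 1 evaluations the baseline evaluations and lists haematology among them (item 8). Section 3.1 also labels Day 1 as baseline. Under the last-assessment-before-dose definition (Section 8.2.2 and SAP Section 3.1.3), a subject on schedule has the same Day 1 draw. The definitions part only if that draw is missed, in which case the screening value becomes baseline.

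3. **When the result exists.** SAP Section 3.6.2 sends haematology to the central laboratory. The sponsor's stated reason for changing criterion 16 is worded for Day 1 blood draws in general, not for liver tests alone. Protocol Section 7.2 expressly allows a local laboratory only for virology. The SAP says local data will be listed, but nothing requires a local blood count before the Day 1 dose.

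4. **When the decision is made.** The heading of Section 6.2 places Day 1 after confirmation of eligibility. Its first item is enrolment. Section 7.6 has the Day 1 morning dose taken in front of site staff.

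5. **Resulting order.** Screening haematology (up to 28 days before Day 1); eligibility confirmed; enrolment; Day 1 pre-dose draw; first dose; central result of the Day 1 draw. The value named in criterion 18 comes last.

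6. **Does another provision close the gap?** Screening haematology is scheduled (Time and Events Table; Section 6.1, item 7), so a result is in hand, but no haemoglobin, platelet or neutrophil limit is attached to it. Inclusion criterion 9 and exclusion criterion 25 let the investigator refuse entry on judgement. That is a safeguard but not a numerical limit.

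The amendment summary is used here only for the sponsor's statement about turnaround. The conflict itself lies in current text: criterion 18 against the baseline definitions, Section 6.2, Section 7.6 and SAP Section 3.6.2.

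**The case against.** The best case for leaving the text alone is that sites can make it work. Baseline is defined mainly for statistical summaries, and the synopsis qualifies its definition. Section 7.1 even calls the screening ECG a baseline ECG. Since eligibility is settled before Day 1, a site might reasonably apply criterion 18 to the latest result available, which is the screening one. That is a possible reading, but the explicit definitions point to Day 1, and the ECG usage does not concern haematology. A fixed entry limit should not depend on which reading a site adopts.

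It may also be said that criterion 16 was a different case, because the amendment summary shows a hepatic criterion that tied baseline to the 24 hours before dosing. The summary has two hepatic entries, however. The text replaced in the entry that moved the criterion to screening said baseline with no 24-hour definition, as criterion 18 still does. The parallel holds.

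Other objections do limit the point. A reader might infer that any subject below the limits will be dosed before anyone can act. The documents do not support that: screening counts are drawn, and a clearly low value would probably be noticed under inclusion 9 or exclusion 25. A reader might also infer that correcting the time point protects subjects from a fall in haemoglobin before the first dose. It does not. A subject who passes at screening and drops below a limit by Day 1 would still be dosed; the only change is that the subject would no longer be ineligible. Nor is there any basis for a rate. Dividing one hypothetical subject by 6 or by 13 does not show how often this would happen.

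Finally, the consequences for analysis are small. SAP Section 6 drops per-protocol analyses, SAP Section 3.3.2 only lists significant deviations, and SAP Sections 1 and 6 record that enrolment was not continued.

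**Conclusion.** The point holds as a defect in an entry rule. As written, criterion 18 names a value that cannot inform the entry decision, and the screening value that could inform it has no numerical limit attached. The sponsor recognised and corrected the same problem in criterion 16.

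Its size is modest and cannot be quantified from the documents. The case that certainly falls through is a subject who is acceptable at screening and below a limit on Day 1, a gap of up to 28 days. The practical gain is an enforceable limit and no ineligibility discovered after dosing. It would not be right to present this as evidence that subjects were put at risk, or as something that changes a planned efficacy summary. With enrolment stopped, what remains live is whether enrolled subjects are judged to have met criterion 18, and on which result, for the deviation listing.

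The conclusion assumes that the turnaround stated in the amendment rationale applies to haematology as it does to liver tests, and that sites were not running local blood counts before the Day 1 dose.

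**What to change.** In criterion 18, in the synopsis and in Section 4.3, replace the baseline time point with one whose result exists before the first dose, so that it agrees with criterion 16 and with the Day 1 laboratory turnaround. Screening haematology is already scheduled, and screening is the time point the sponsor chose for criterion 16. Keep the Day 1 draw as the reference for change-from-baseline summaries and for the rules that measure change from baseline. The haematological limits themselves are not in question here.

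The cost is two words in two places, with no added sample or visit. The price is that a fall between screening and Day 1 is no longer an entry failure; under the current text it could not stop the first dose either. If enrolment does not reopen, a sentence in the abbreviated study report saying which haematology result was used to judge criterion 18 would serve the deviation listing.

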### **Study Medication**

CCX140-B will be administered as 5 mg CCX140-B tablets

